2.1 Objectives and Endpoints/Estimands

Objec	tives	Endpoints			
Prima	Primary				
•	To evaluate the efficacy of apremilast 30 mg twice daily (BID) compared with placebo in subjects with PPP	 Achieving at least 50% reduction from baseline in Palmoplantar Pustulosis Area and Severity Index (PPPASI) total score (PPPASI-50) at week 16 			
Seco	ndary				
•	To evaluate the efficacy of apremilast 30 mg BID compared with placebo in subjects with PPP	 Change from baseline in PPPASI total score at week 16 Change from baseline in Palmoplantar Pustulosis Severity Index (PPSI) total score at week 16 Change from baseline in subject's Visual Analogue Scale (VAS) assessment for PPP symptoms (pruritus and pain/discomfort) at week 16 Change from Baseline in Dermatology Life Quality Index 			
		(DLQI) total score at week 16			
•	To evaluate the safety and tolerability of apremilast 30 mg BID compared with placebo in subjects with PPP	 Treatment-emergent adverse events (TEAEs), serious TEAEs, and TEAEs of interest Clinically significant changes in body weight, vital signs, and laboratory abnormalities 			

Primary Estimand

The main estimand of primary interest for the primary efficacy endpoint (i.e., achievement of PPPASI-50 response defined as at least 50% reduction from baseline in PPPASI total score, at week 16) is defined in terms of the following attributes:

- The target population of interest is Japanese subjects with PPP defined through the inclusion/exclusion criteria.
- The primary endpoint is the achievement of PPPASI-50 response at week 16.
- Intercurrent events (IEs) are investigational product (IP) discontinuation due to lack of efficacy, adverse event, or protocol-prohibited medication use. A subject will be considered a treatment failure after any of the IEs.
- The summary measure is the difference between apremilast 30 mg BID group and placebo group in proportion of responders based on the intent-to-treat (ITT) population including all randomized subjects.

A missing value after any of the IEs will be imputed as non-responders, otherwise, will be imputed with a multiple imputation (MI) method. A non-missing value after any of the IEs will also be imputed as non-responders.

Secondary Estimand(s)

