5.5 Analysis Phases

• Placebo-controlled Phase/Period – Weeks 0 to16

This period starts on the day of randomization (Week 0/Visit 2), and stops on below:

(1) the day of Week 16/Visit 8 if the subject continued study treatment to the active treatment phase

(2) the day of the discontinuation if the subject discontinued study treatment prior to or at Week 16/Visit 8

(3) the last known study day if the subject is lost to follow-up prior to or at Week 16/Visit 8

• Active Treatment Phase/Period – Weeks 16 to 52

This period starts on one day after the day of the dose of apremilast distributed at Week 16/Visit 8, and stops on either below.

(1) the day of Week 52/Visit 13

(2) the day of the discontinuation if the subject discontinued prior to or at Week 52/Visit13

(3) the last known study day if the subject lost to follow-up prior to or at Week 52/Visit 13 during the phase

For safety analysis, the period starts on the day of the first dose of apremilast in the period.

• Safety Follow-up Phase/Period

Subjects who complete or discontinue the study treatment, will be followed up for 30 days after the end of treatment visit.

For adverse event analysis, data from the first 30 days after the last dose of IP will be included in the precedent treatment phase and data after the 30 days will be presented separately.

• Apremilast exposure period

This period starts on the date of either:

- the first dose of IP following randomization (Week 0/Visit 2) for subject who are treated with apremilast from Week 0

- the first dose of IP from the IP dispensed at Week 16/Visit 8 for subjects who were originally treated with placebo and are switched to apremilast at Week 16

This period stops on either: (1) data restriction date; or (2) the end of the study.

During the apremilast-exposure period, data are presented by treatment sequence, i.e., Placebo/30 mg BID, 30 mg BID as Initiated, and a total column of 30 mg BID as Treated.

6. Populations for Analysis

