9.2 Subject Accountability

Frequency summary of subjects randomized, screened but not randomized among all screened subjects will be provided. The frequency of subjects who failed each inclusion/exclusion criteria will be included in the summary.

The number and percentage of subjects included in the ITT and safety analysis population will be summarized.

Subject disposition will be provided for placebo-controlled period and active treatment period based on ITT population respectively. Summary of safety follow-up period and study completion will be included in each disposition summary. The summaries include the number and percentage of subjects who entered the period, who completed the period, who completed IP, who ended IP and study with the reason. Subjects who ended IP are considered to enter the safety follow-up period unless the subjects ended the study on the same day.

Key study dates for the first subject screened and enrolled (randomized), last subject enrolled (randomized), data cut-off (last subject's week 16 and 24 visit), last subject end of IP, last subject end of study will be presented.

The number and percentage of subjects randomized will be tabulated by study site.

Listings of subject accountability will be provided.

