9.5.1 Analyses of Primary Efficacy Endpoint(s)/Estimand(s)

The primary efficacy endpoint is the achievement of PPPASI-50 response at week 16. The proportion of subjects achieving PPPASI-50 response in apremilast 30 mg BID group and placebo group will be compared using Cochran-Mantel-Haenszel (CMH) test adjusting for the stratification factors for randomization [PPPASI total score range ($\leq 20 / 21-30 / \geq 31$) at baseline and subject's focal infection status (yes/no) at baseline]. The testing will be conducted at the 2-sided 0.05 significance level. Subjects who discontinue IP prior to week 16 due to lack of efficacy, adverse event, or use of protocol prohibited medication will be considered as treatment failures as the result of the IE and the PPPASI-50 values for visits on and after the IE will be imputed as non-responders. The missing data (PPPASI total score) due to other reasons will be imputed using MI method.

The two-sided p-values from the CMH test, the adjusted treatment difference in proportion using the weighted average of the treatment differences across the strata with the CMH weights, along with the associated two-sided 95% CIs using a normal approximation to the weighted average will be provided. Similarly, unadjusted treatment differences in proportions will also be provided.

Sensitivity analyses for the primary endpoint will be conducted using the non-responder imputation (NRI) method for any missing data **due to other reasons (not IE)**. Additionally, to assess sensitivity to departures from the missing data assumption (MAR), the tipping point analysis will be performed. Another sensitivity analysis for the primary endpoint will be performed based on data-derived stratification factors.

For MI method, the SAS procedure MI will be used to impute missing PPPASI scores at the scheduled analysis visits in the Placebo-controlled Phase (Week 0-16) to create M=50 complete datasets. The missing data patterns will be checked at the scheduled

analysis visits, i.e., Baseline (week 0), week, 2, 4, 6, 8, 12, and 16. If there are nonmonotone missing patterns, two separate imputation procedures will be used to complete the imputation process.

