Appendix B. Analytical Windows

Per protocol, visits are to be performed within 2 days of the protocol-specified study day for placebo-controlled period, and within 4 days for the active treatment period. To allow for variations in scheduling, the following visit windows will be applied to selected efficacy evaluations to assign a most appropriate nominal visit for analysis. If more than one assigned visit falls within the same defined window, the closest visit to the target day (ie, scheduled visit week × 7 + 1) will be considered for analysis. If two assessment dates are the same distance from the target day, then the latest visit will be considered for analysis.

Vital Signs and Physical Measurement

Visit Week	Target Day	Window Definition
Week 0 (Visit 2: Baseline)	1	Last Evaluation prior to or on Study Day 1
Placebo-controlled Period	-	
Week 2 (Visit 3)	15	Study Day 2 – 22
Week 4 (Visit 4)	29	Study Day 23 – 36
Week 6 (Visit 5)	43	Study Day 37 – 50
Week 8 (Visit 6)	57	Study Day 51 – 71
Week 12 (Visit 7)	85	Study Day 72 – 99
Week 16 (Visit 8)	113	Study Day 100 – End of the Period
Active Treatment Period		
Week 20 (Visit 9)	141	One day after the first apremilast dosing day on Visit 8* – 155
Week 24 (Visit 10)	169	Study Day 156 – 197
Week 32 (Visit 11)	225	Study Day 198 – 267
Week 44 (Visit 12)	309	Study Day 268 – 337
Week 52 (Visit 13)	365	Study Day 338 – End of the Period

Analysis window for Subject's VAS assessment for PPP symptom for palms and soles

Visit Week	Target Day	Window Definition
Week 0 (Visit 2: Baseline)	1	Last Evaluation prior to or on Study Day 1
Placebo-controlled Period		
Week 2 (Visit 3)	15	Study Day 2 – 22
Week 4 (Visit 4)	29	Study Day 23 – 36
Week 6 (Visit 5)	43	Study Day 37 – 50
Week 8 (Visit 6)	57	Study Day 51 – 71
Week 12 (Visit 7)	85	Study Day 72 – 99
Week 16 (Visit 8)	113	Study Day 100 – End of the Period
Active Treatment Period		

Visit Week	Target Day	Window Definition
Week 24 (Visit 10)	169	One day after the first apremilast dosing day on Visit 8 – 197
Week 32 (Visit 11)	225	Study Day 198 – 295
Week 52 (Visit 13)	365	Study Day 296 – End of the Period

Analysis window for DLQI, and Laboratory Test

Visit Week	Target Day	Window Definition			
Week 0 (Visit 2: Baseline)	1	Last Evaluation prior to or on Study Day 1			
Placebo-controlled Period					
Week 8 (Visit 6)	57	Study Day 2 – 85			
Week 16 (Visit 8)	113	Study Day 86 – End of the Period			
Active Treatment Period					

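### Read literally, SAP 5.5 and Appendix B leave a week 16 VAS or DLQI value without an analysis slot when it is collected after a treatment stop that is not an intercurrent event, so it would be handled as missing

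*SAP*

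**What the plan says.** SAP 5.5 runs the placebo-controlled period to Visit 8 only for subjects who go on to active treatment. For those who stop treatment, the period ends on "the day of the discontinuation if the subject discontinued study treatment prior to or at Week 16/Visit 8". Item 2 does not distinguish reasons for stopping.

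In Appendix B the week 16 row is "Study Day 100 – End of the Period" for VAS and "Study Day 86 – End of the Period" for DLQI. The next row for both, week 24, opens the day after a first apremilast dose at Visit 8.

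SAP 5.5 carries data past the stop explicitly for one purpose: "For adverse event analysis, data from the first 30 days after the last dose of IP will be included in the precedent treatment phase". SAP 9.2 adds: "Subjects who ended IP are considered to enter the safety follow-up period unless the subjects ended the study on the same day".

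The estimand in SAP 2.1 is narrower: "Intercurrent events (IEs) are investigational product (IP) discontinuation due to lack of efficacy, adverse event, or protocol-prohibited medication use". On missing data it says: "A missing value after any of the IEs will be imputed as non-responders, otherwise, will be imputed with a multiple imputation (MI) method". For the secondary endpoints, SAP 9.5.2 leaves data missing for other reasons unimputed, relying on the MMRM under MAR.

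Protocol 7.1 wants subjects who stop treatment kept on study, where safe and feasible, so that outcomes can be collected. Protocol 7.2 includes subject data in the analysis up to withdrawal of consent.

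**The concern.** Protocol 7.1 lists reasons for stopping that are not intercurrent events: subject request, sponsor decision, pregnancy, and protocol deviations other than prohibited medication. A subject who stops for one of these and still attends around week 16 supplies the value that the estimand asks for. Read literally, the period definition gives that value nowhere to go, and the analysis then uses a model-based prediction in its place. No text in the estimand sanctions this, since MI and MAR are there for values that are missing.

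Three of the five secondary endpoints in the fixed sequence are touched directly (pruritus VAS, pain/discomfort VAS and DLQI). SAP Table 9-2 rules out sensitivity analyses for the secondary endpoints, so nothing planned would show the effect. PPPASI and PPSI, and with them the primary endpoint, would be touched only if the same period end governs their week 16 visit.

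**Working it through.** **Window check.** Inputs: the period end in SAP 5.5 item 2, the week 16 rows of Appendix B, and target Day 113. Suppose the value is collected on Day 113 by a subject who stopped treatment earlier.

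| Treatment stop | VAS week 16 window | Day 113 value |
|---|---|---|
| Day 60 or Day 99 | empty | no slot |
| Day 105 | Days 100–105 | no slot |
| Day 112 | Days 100–112 | no slot |
| Day 113 or later | Day 100 to stop day | in window |

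For DLQI the window starts on Day 86, and Day 113 is again outside for any stop before Day 113. The week 24 row cannot take the value, because this subject never takes the Visit 8 apremilast dose that opens it. Two things are not cut: a value taken on the stop day itself from Day 100 (DLQI: Day 86), and the VAS windows for weeks 2 to 12 and the DLQI week 8 window, which have fixed study-day limits.

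**PPPASI and PPSI.** No readable table in Appendix B names them. The link is SAP 9.5.1, which uses MI to "impute missing PPPASI scores at the scheduled analysis visits in the Placebo-controlled Phase (Week 0-16"). If that phase ends as in SAP 5.5, PPPASI-50 goes to MI and the PPPASI and PPSI changes go to the MMRM. This is an inference.

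**Reproducing the plan's power.** Inputs from SAP 3.2: 40% and 65%, 85 per group, 2-sided alpha 0.05. With mean rate 0.525:

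Φ[(0.25 × √85 − 1.96 × √(2 × 0.525 × 0.475)) / √(0.65 × 0.35 + 0.40 × 0.60)] = Φ[(2.305 − 1.384) / 0.684] = Φ(1.347) = 91.1%.

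The stated 90% is reproduced. With 81 per group (about 5% without a usable value) power is 89.7%. The point does not change the planned sample size.

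**Size for PPPASI-50, if the inference holds.** Let k be the subjects per arm who stop for a reason that is not an intercurrent event and still give a week 16 value. The documents do not give k. Assumptions: equal k in both arms, equal off-treatment response r in both arms, and MI imputing at the planned 65% and 40%.

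- Shift = k/85 × (65 − r) − k/85 × (40 − r) = k/85 × 25 points.
- k = 0: 0. k = 1: 25/85 = 0.29.
- Illustrative outer case, k = 5% × 85 = 4.25: 4.25/85 × 25 = 1.25. The plan's 5% is dropout, and subjects who leave the study have no value to discard, so this overstates k.
- Planned 95% CI half-width = 1.96 × √[(0.65 × 0.35 + 0.40 × 0.60)/85] = 0.145, or 14.5 points. So k = 1 is 0.29/14.5 = 2% of it and k = 4.25 is 1.25/14.5 = 9%.
- The direction is not fixed. With r assumed between 20% and 40%, one such subject on apremilast only gives 1/85 × (65 − r) = +0.29 to +0.53. One on placebo only gives −1/85 × (40 − r) = −0.24 to 0.

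MI also conditions on previous visits, so the real shift may be smaller. The documents give no SD for the VAS or DLQI, so no figure is offered for them.

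**The case against.** The strongest reply is that the SAP does not treat a treatment stop as a data cut-off. SAP 2.1 says what to do with non-missing values after an intercurrent event, and SAP 9.5.2 overrides observed data from the event up to week 16. Every intercurrent event is a treatment stop, so the authors expected values after a stop. The period is also labelled weeks 0 to 16, Appendix B says its windows exist to allow for scheduling variation, and nowhere is a value outside a window declared missing. This stands as evidence that the cut is unintended. It does not supply a rule that keeps the value: the literal wording excludes it, and no other section says how it is used.

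A second reply is that few such values will exist. Table 1-1 footnote a sends subjects who stop to an ET visit and 30-day follow-up, and Protocol 7.1 requires only a discussion of continuing the schedule. This limits the size, and it largely stands. It is not complete, because Protocol 7.1 does allow the schedule to continue. Table 1-1 also schedules PPPASI, PPSI and VAS at the safety follow-up visit: a last dose on Day 83 puts that visit on about Day 113 (83 + 30).

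A reader might also infer that a Visit 8 value is lost whenever the last dose was taken the day before. The documents do not support this. SAP 5.5 item 2 covers stopping at Visit 8 as well as before it, and SAP 5.1.1 names the last dose and the treatment discontinuation date as separate dates. One clarifying sentence is enough.

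**Conclusion.** The point holds on a literal reading for VAS and DLQI: a week 16 value collected after a stop that is not an intercurrent event has no slot and falls to MAR handling, against the estimand, Protocol 7.1 and 7.2, and the SAP's own references to observed values after a stop. That the value is treated as missing follows from combining the rules; the SAP does not say so outright.

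Two stronger readings are tempting. One is that the primary analysis discards observed PPPASI-50 outcomes. The documents do not show this, because no readable window table covers PPPASI or PPSI. The other is that the rule biases the trial towards apremilast. The number affected is unknown and may be close to zero, and the direction depends on which arm the subjects are in. About 0.3 points for one subject per arm rests on equal numbers and equal off-treatment response across arms, with imputation at the planned rates.

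The NRI and tipping-point analyses in SAP 9.5.1 help to bound any effect on the primary endpoint. The secondary endpoints have no such check. Low priority.

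**What to change.** In SAP 5.5 and Appendix B:

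- State that, for efficacy, the week 16 window of a subject who stopped treatment earlier does not close at the stop. Close it at the attended Visit 8, or at a study-day limit near target Day 113 that is comparable with continuing subjects, whose period ends at Visit 8 (allowance ±2 days, so Days 111–115). A limit as late as Day 141, the midpoint of Days 113 and 169, would give those who stopped a much wider week 16 window than those who continued.
- Use values collected in that window after a stop that is not an intercurrent event as observed. Apply MI or the MMRM's MAR handling only to values not collected. Leave the intercurrent-event rules unchanged.
- State that these rules also cover PPPASI and PPSI, and whether a safety follow-up score falling in the window counts.
- State that discontinuation in SAP 5.5 does not mean the last-dose date, so that a Visit 8 value is kept.

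Reconcile Protocol Table 1-1 footnote a with Protocol 7.1 on visits after a treatment stop. If dropping these values is intended, say so in the estimand text.

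The cost is SAP wording and minor programming before the week 16 lock, plus a protocol clarification for the footnote. No new assessments are needed.

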7.1 Discontinuation of Study Treatment

Subjects (or a legally authorized representative) can decline to continue receiving investigational product and/or other protocol-required therapies and/or procedures at any time during the study but continue participation in the study. If this occurs, the investigator is to discuss with the subject the appropriate processes for discontinuation from investigational product or other protocol-required therapies and must discuss with the subject the possibilities for continuation of the Schedule of Activities (see Table 1-1) including different options of follow-up (eg, in person, by phone/mail, through family/friends, in correspondence/communication with other treating physicians, from the review of medical records) and collection of data, including endpoints, adverse events, and must document this decision in the subject's medical records. Subjects who have discontinued investigational product and/or other protocol-required therapies and/or procedures should not be automatically removed from the study. Whenever safe and feasible, it is imperative that subjects remain on-study to ensure safety surveillance and/or collection of outcome data.

Reasons for early removal from protocol-required investigational product(s) or procedural assessments may include any of the following:

- decision by Sponsor
- lost to follow-up
- death
- adverse event
- subject request
- lack of efficacy
- protocol deviation
- pregnancy

Protocol Number: 20200195

Date: 15 April 2022 Page 41 of 99

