5.1 Safety Related Definitions

5.1.1 Treatment-emergent Adverse Events (TEAEs)

Any AEs that begin or worsen on or after the first dose of IP through 30 days after the last dose of IP or study treatment discontinuation date, whichever is later.

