9.6.1 Analyses of Primary Safety Endpoint(s)

There is no primary safety endpoint. As a secondary endpoint, the safety and tolerability of apremilast 30 mg BID will be compared to placebo. No inferential testing for statistical significance will be performed for safety analyses.

Unless otherwise specified, the analyses of AEs and marked abnormalities (laboratory parameters and vital signs) for both the placebo-controlled period and apremilast-exposure period will be summarized by subject incidence rate. For safety summaries of apremilast-exposure period, the exposure-adjusted incidence rate will be presented to account for the difference exposure to the IP.

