9.6.3 Laboratory Test Results

Summary statistics of observed values and changes from baseline in the selected laboratory parameters will be provided over time. Frequency summary of shifts from baseline to the worst post-baseline value in terms of normal/abnormal will be provided. The selected laboratory parameters with abnormalities criteria are available in the Appendix A. For the purposes of the summary, subjects with abnormal (normal) values at baseline are defined as those whose baseline value is low (not low) for criteria concerning low values and those whose baseline value is high (not high) for criteria concerning high values; both low and high are relative to the laboratory normal range.

Individual subject data of all laboratory data will be listed and values outside of the normal reference range will be flagged.

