9.6.4 Vital Signs

The analyses of vital signs including summary statistics **of observed values and changes from baseline** over time will be provided. Frequency summaries of shifts from baseline to the worst post-baseline value in terms of normal/abnormal(low/high) will be provided for **heart rate** and blood pressure. Normal ranges are defined as: 60-90 mmHg for diastolic blood pressure, 90-140 mmHg for systolic blood pressure, and 60-100 beats/minute for **heart rate**.

A subject data listing of all vital signs will be provided.

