9.6.6 Exposure to Investigational Product

Descriptive statistics will be produced to describe the exposure to IP by treatment group. Treatment duration (in weeks) is calculated as (the date of the last dose of IP – the date of the first dose of IP + 1)/7. Summary statistics for treatment duration (in weeks), as well as a frequency summary of treatment duration categories (placebo-controlled period: < $4, \ge 4$ to < $8, \ge 8$ to < $12, \ge 12$ to < $16, \ge 16$, active treatment period: ≥ 16 to < $20, \ge 20$ to < $24, \ge 24$ to < $32, \ge 32$ to < $44, \ge 44$ to < $52, \ge 52$ weeks) will be provided.

Treatment duration for apremilast-exposure period is calculated from the date of the first apremilast administered, which is the date of the first administration of apremilast on/after the randomization at week 0 (visit 2) or switched to apremilast at week 16 (visit 8), to the last apremilast administered date of subjects who discontinue before the study completion or who complete the study at week 52 (visit 13).

For treatment compliance, descriptive statistics will be provided. The treatment compliance (%) for each subject will be computed as 100 times the total number of tablets actually taken (sum of dose per administration) over the period divided by the intended total number of tablets that should have been taken over the same period. It is assumed that a subject takes 2 tablets per day from the first through the last IP administered date.

A subject data listing of IP administration will be provided.

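### SAP 5.5 gives the apremilast exposure period no end tied to the last dose, so off-drug laboratory and vital-sign values can enter its marked-abnormality and worst-value tables

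*SAP*

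**What the plan says.** SAP 5.5 starts the apremilast exposure period at the first apremilast dose (week 0 for starters, week 16 for subjects switched from placebo) and ends it as follows: "This period stops on either: (1) data restriction date; or (2) the end of the study". In the same section, the placebo-controlled and active treatment periods do end on the day a subject discontinues.

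A limit after the last dose exists for adverse events. SAP 5.1.1 defines treatment-emergent events as "Any AEs that begin or worsen on or after the first dose of IP through 30 days after the last dose of IP" (or the treatment discontinuation date, if later). For adverse event analysis, SAP 5.5 says that "data from the first 30 days after the last dose of IP will be included in the precedent treatment phase", with later data shown separately. I find no matching rule for laboratory or vital-sign data.

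Those data are nevertheless summarised for this period. SAP 9.6.1 says that "marked abnormalities (laboratory parameters and vital signs) for both the placebo-controlled period and apremilast-exposure period will be summarized by subject incidence rate", and adds exposure-adjusted rates for exposure-period safety summaries. SAP 9.6.3 (laboratory) says "Frequency summary of shifts from baseline to the worst post-baseline value in terms of normal/abnormal will be provided". SAP 9.6.4 does the same for heart rate and blood pressure: "Frequency summaries of shifts from baseline to the worst post-baseline value in terms of normal/abnormal(low/high) will be provided". SAP 9.6.6 runs treatment duration in this period "to the last apremilast administered date of subjects who discontinue before the study completion", or to week 52 for completers.

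The documents differ on what happens after a subject stops treatment. Footnote a of Protocol Table 1-1, Protocol 8.1.3, SAP 5.5 and SAP 9.2 lead to a safety follow-up of about 30 days. Protocol 7.1 says: "Whenever safe and feasible, it is imperative that subjects remain on-study to ensure safety surveillance and/or collection of outcome data".

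**The concern.** A worst-value or any-abnormality table takes every qualifying value inside its window. If the window runs past the end of dosing, a value measured after the drug was stopped is reported as an apremilast finding. Subjects who stop early have the least on-drug time, so they are the most exposed to this, and they are also the subjects whose safety data matter most.

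The exposure-adjusted rates have a related problem. SAP 9.6.2 builds exposure time from treatment duration, which ends at the last dose. If marked abnormalities are counted to the end of the study, numerator and denominator cover different time spans.

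At stake is the descriptive long-term safety account. SAP 7.3 and 7.4 do not repeat the placebo-controlled analyses at week 24 or at the final analysis, so the later laboratory and vital-sign description rests largely on this period. Laboratory and vital-sign changes are also part of a secondary safety endpoint.

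**Working it through.** **Inputs from the documents.** Screening 4 weeks; treatment to week 52; visit 14 at 30 days after the last dose with a +7-day allowance (Protocol Table 1-1, 8.1.3). Laboratory tests and vital signs are both scheduled at visit 14. Time on apremilast for a completer is 52 × 7 = 364 days for a starter and 36 × 7 = 252 days for a switcher.

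**The plan's own figure.** 4 + 52 + 30/7 = 60.3 weeks (61.3 with the +7 days), which matches the stated duration of about 60 weeks. A completer's end of study therefore lies 30 to 37 days after the last dose.

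**Reach on the usual path (safety follow-up only).** Off-drug days divided by on-drug days:

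- Starter who completes: 30/364 = 8.2% to 37/364 = 10.2%
- Switcher who completes: 30/252 = 11.9% to 37/252 = 14.7%
- Starter who stops at week 12: 30/84 = 35.7% to 37/84 = 44.0%
- Starter who stops at week 4: 30/28 = 107% to 37/28 = 132%

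In each case this is one scheduled off-drug follow-up visit.

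**Reach if a starter stays on study to week 52 under Protocol 7.1.** Off-drug days = 364 − days on drug:

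- Stop at week 4: 364 − 28 = 336 days (12 times on-drug time)
- Stop at week 12: 364 − 84 = 280 days (3.3 times)
- Stop at week 24: 364 − 168 = 196 days (1.2 times)

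With full attendance, which is an assumption, a starter who stops at week 8 has 4 of the 5 laboratory draws at weeks 8, 16, 24, 32 and 52 off drug, and 7 of the 11 vital-sign records from week 2 to week 52. Visit 14 is left out of these counts.

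**Whole study, on assumptions.** Take 85 starters and 85 × 0.95 = 80.75 switchers, using the planned 5% double-blind dropout. With no early stops, on-drug time is 85 × 52 + 80.75 × 36 = 7,327 weeks. Off-drug time is 165.75 × 30/7 = 710 weeks to 165.75 × 37/7 = 876 weeks, so 9.7% to 12.0%. Now assume that 5% to 20% stop early, after 12 weeks on apremilast for starters and 8 for switchers. The share is then 10.1% to 14.1% with safety follow-up only, and 13.6% to 27.5% if all of them stay to week 52 (30-day follow-up used for completers). The stop rates and times are not in the documents.

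**Why nothing else closes the gap.** The Appendix B windows sit under the placebo-controlled and active treatment periods, so they bound by-visit summaries. They do not expressly limit worst-value or marked-abnormality tables for the exposure period. SAP 5.5 also leaves open whether its end of study is the Study End Date (5.2.6) or the subject-level date (5.2.7), and I find no definition of the data restriction date.

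**The case against.** The strongest reply is that values long after the last tablet are not the planned case. Four places send a subject who stops treatment into a follow-up of about 30 days. Protocol 7.1 only asks the investigator to discuss continuing the schedule, and its options include telephone, mail and medical records, several of which yield no scheduled blood draw. This stands. A reader might infer that long-delayed off-drug values routinely count as apremilast findings, but the documents support that only for subjects retained with in-person visits.

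A reader might also infer that recovery of weight after stopping would dilute a weight-loss signal. The documents do not support this. SAP 9.6.5 gives weight and BMI only observed values and changes from baseline, the exposure-period baseline rule in SAP 5.3.3 does not name weight, and the weight windows in Appendix B close with periods that end at discontinuation.

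Nor does SAP 9.6.6 contradict SAP 5.5 as such. One defines treatment duration and the other a data window, and a window somewhat longer than dosing is normal, as the adverse event rule shows. The mismatch matters only where both enter the same rate.

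Later values might be taken on another systemic drug. Table 6-2 bars such drugs until the end of active treatment and does not say whether that ends for an individual who stops, so this is possible but not established.

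Finally, the summaries are descriptive and all the data are listed. That limits the stakes, but it does not supply the missing cut-off.

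**Conclusion.** The gap is real and of moderate consequence. Followed as written, the SAP lets off-drug laboratory and vital-sign values into the marked-abnormality and worst-value tables for apremilast, and any exposure-adjusted rate for them would use time that stops earlier than the counting does.

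The reach is normally one visit at 30 to 37 days. It becomes months only under retention with in-person visits, and how often that would happen is unknown. A specific rise in abnormality incidence would need abnormality rates on and off drug, stop rates and attendance after stopping. Beyond the 5% double-blind dropout figure the documents give none of these, so no such number should be attached to the point. Adverse events, including the weight-decrease event of interest, already have their 30-day limit. The primary efficacy analysis and the sample size are not affected.

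**What to change.** In SAP 5.5, for laboratory and vital-sign marked-abnormality and worst-value summaries, end the apremilast exposure period at the earliest of:

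- the data restriction date (to be defined);
- the subject-level end of study date (SAP 5.2.7);
- a fixed interval after the last apremilast dose that covers the scheduled safety follow-up visit, that is 30 + 7 = 37 days.

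A hard 30-day cut would split visit 14: a sample on day 30 would stay and one on day 31 would move, although both come from the same planned visit. Show later values separately, as SAP 5.5 already does for adverse events. For exposure-adjusted rates of these abnormalities, count events and time over the same window.

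With this rule, off-drug time inside the period is at most 37 days per subject, against up to 280 days for a week-12 stopper retained to week 52.

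Separately, reconcile Protocol 7.1 with footnote a of Table 1-1 and with SAP 5.5 and 9.2, so that it is clear which visits a subject has after stopping treatment.

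The cost is a short addition to the SAP and one date condition in the derivation. A few late off-drug values move to a separate display, and no data are lost.
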